#### **6.1.4 Accountability**

Documentation of receipt, study product inventory, and return shipments of the study product must be maintained at each study site. Upon receipt of the study product supplies, an inventory must be performed. It is important that site personnel count and verify that the shipment contains all the items noted in the shipment record and that they are in good condition. At study completion, all containers of study product, used and unused, must be returned to the Sponsor or designee, or destroyed with the Sponsor's approval.

In addition, a study product accountability log showing dispensing to and return by subjects must be maintained at each study site. Any dispensed tubes that are not returned to the clinic must be documented on the log.

#### **6.1.5 Storage**

The study product must be stored at controlled room temperature 20°-25°C (68°-77°F); excursions permitted to 15°-30°C (59°-86°F).

The Investigator agrees to use the study product only within the framework of this clinical study and in accordance with this study protocol. Any unused, partially used or empty containers of the study product will be returned to the Sponsor or destroyed with the Sponsor's approval after drug accountability has been done at the termination of the study.

Receipt, distribution and return of the study product must be properly documented on the drug accountability form.

### **6.2 Treatment Regimen**

Subjects will use assigned study product twice daily (i.e. in the morning and in the evening, after any bathing or showering) with approximately 12 hours between applications for 12 consecutive weeks starting from Baseline/Day 1 (Visit 2) during the study visit. After randomization during the Baseline/Day 1 Visit (Visit 2), subjects will apply the first dose of study medication in the Investigator's office under supervision. The area(s) of application must be washed (with an Investigator-approved cleanser) before the study product is applied. Subjects should be instructed to apply a dime size amount of study product to the Investigator identified single contiguous treatment area (5 cm x 5 cm). Subjects will be provided with a diary to record the timing of application of the study medication on a daily basis. Starting with the first application during the Day 1 Visit, all applications will be recorded in the subject diary, which

---

will be checked by the Investigator or designee for compliance and potential safety-related data at Visits 3-6.

### **6.3 Treatment Precautions**

Study products should not be used by any subject with known or suspected hypersensitivity to any non-steroidal anti-inflammatory drugs (NSAIDs) or any component of the formulation of the study medication. Indications of hypersensitivity include a history of asthma, uticarial, or other allergic-type reactions after taking aspirin or other NSAIDs or known or suspected allergy to sulfonamides.

### **6.4 Treatment and Protocol Compliance**

Subjects will be provided an instruction sheet for the study product along with a diagram of affected areas to be treated. Study staff should review the instruction sheet and diagram with the subjects at every visit to ensure protocol compliance. AK lesions are to be counted and updated within the treatment area on the diagram at each post-Baseline visit. The first and last application of study product will be performed by the subjects at the site under supervision.

At each post-Baseline visit until Visit 5, the Investigator or designee will interview subjects concerning treatment compliance and ask if any doses have been missed. The Investigator will also ask about compliance with protocol requirements. Protocol deviations will be recorded in the subject's study record, and on a protocol deviation form that will be provided to the site. These items may also be apparent from the missing data on the CRF and will be identified programmatically during data analysis for purposes of reporting. The Sponsor should be consulted before discontinuing subjects due to protocol deviations unless safety is a concern.

Subjects will be provided a diary card for documenting the dates of applications. The subjects will review the diary card with the Investigator or designee at each visit. The number of applications applied and the number of missed applications will be recorded on the source documents. By definition, there are no missed applications after the last date of treatment even if recorded on the diary.

In addition, tubes of study product will be weighed before dispensing and after the return of the investigational products. At the last visit, the tube should be weighed before and after the application to determine the amount of study product applied for the last dose. These weights should be entered into the CRF.

### **6.5 Method of Assigning Subjects to Treatment Groups**

Subjects will be assigned randomly via IWRS to one of four treatment groups in a 1:1:1:1 ratio (60 subjects per treatment group). A study medication assignment schedule will be created that is stratified by site, with kit numbers randomly assigned to study products. A randomization schedule will be produced for each site independently for use in randomization by the IWRS. The date and time of randomization, as well as the kit number, will be entered on the eCRF.

The Investigator shall ensure that the study product is only used by subjects under the Investigator's personal supervision or under the supervision of a sub-investigator responsible to the investigator and in accordance with the protocol.

## 6.6 Blinding

### 6.6.1 Method of Blinding

This is a multi-center, randomized, double-blind, parallel group, Vehicle-controlled study. The DFD-07 (celecoxib) Cream and Vehicle Cream are white to off-white in color, and are similar in appearance, smell, and feel. The study medication kits (active and vehicle) will be marked for AM and PM use, so as to ensure blinding of the QD versus BID arms of the study. In the QD arms for the active product, the active product marked PM will be applied in the evening while the vehicle product marked AM will be applied in the morning. Since the active and vehicle product are similar, the study blind is expected to be preserved by this approach.

### 6.6.2 Unblinding

This is a double-blind study so neither Investigator nor subject will know which medication they receive. DFD-07 (celecoxib) Cream, 1.25% and 2.5%, and its matching Vehicle for DFD-07 Cream will be similar in appearance and have identical packaging.

The blind should be broken for all subjects suffering serious adverse events (SAEs) in which knowledge of the treatment assignment is critical to the subject's management. The blind for the subject may be broken by the Investigator, or designee, by contacting the IWRS. The blind should not be broken at the study site level except in a medical emergency (where knowledge of the study medication received would affect the treatment of the emergency). For a medical emergency, the blind must only be broken following discussion with Sponsor medical monitor, on a case-by-case basis, at the discretion of the Investigator/treating physician/Sponsor.

If the blind is broken, the date, time, and reason must be recorded in the subject's source record, eCRF, and any associated adverse event (AE) report. If an Investigator, site personnel performing assessments, or subject is unblinded, the unblinding incident and unblinded subject must be listed as a major protocol deviation. A subject for whom the blind is broken will discontinue study medication and be scheduled for an End of Study safety follow-up visit and then discontinued from the study. The subject will be encouraged to stay in the study until the AE is resolved or stabilized. All Investigators and the IRB will receive blinded safety reports. However, on the request of the IRB, the Sponsor will send unblinded reports directly to the IRB.

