#### **8.4 Reporting Serious Adverse Events**

SAE information must be faxed or e-mailed within 24 hours of becoming aware of the event. The minimum *initial* information required to be reported on the Serious Adverse Event Form is: the protocol number, site number, subject number, subject initials, the event, the causality, the date of the event and the name and contact information (email, phone number) of the person reporting the event. This initial report should be promptly followed up with a *completed* Serious Adverse Event Form.

**Serious Adverse Events:** [name]., M.S.

[contact]

Email: [[contact]](mailto:[contact])

The initial information must include a causality assessment that is provided by the primary Investigator or other medically qualified individual. The causality assessment can be amended as more information is available. Significant new information about ongoing SAEs should be reported promptly to the Sponsor.

Serious adverse events will be evaluated by the Medical Monitor within 24 hours of receipt and plans for management and further reporting (i.e. FDA) determined.

It is the responsibility of the CRO, Integrium, LLC® to promptly notify the other Investigators involved in this study and they in turn notify their respective IRBs about serious and unexpected SAEs for which there is a reasonable possibility of their being related to the investigational product.

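### Protocol 6.6.2 makes an emergency code break at a site depend on reaching the Sponsor medical monitor, with no fallback and no named final authority

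*Protocol*

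**What the plan says.** The rule for breaking the blind sits in one paragraph of Protocol section 6.6.2, in four steps.

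- **When:** "The blind should be broken for all subjects suffering serious adverse events (SAEs) in which knowledge of the treatment assignment is critical", meaning critical for how that person is managed.
- **Who and how:** "The blind for the subject may be broken by the Investigator, or designee, by contacting the IWRS".
- **Limit at site level:** "The blind should not be broken at the study site level except in a medical emergency", explained there as one whose treatment would be affected by knowing the study medication.
- **Condition in that emergency:** "For a medical emergency, the blind must only be broken following discussion with Sponsor medical monitor, on a case-by-case basis". The sentence closes by placing the decision "at the discretion of the Investigator/treating physician/Sponsor".

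The same section then requires the date, time and reason for any code break to be recorded, and has the unblinding of an Investigator, assessing site staff or a subject listed as a major protocol deviation. SAP section 2.7.1 mentions unblinding only at the final analysis. No other section of either document returns to emergency unblinding.

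**The concern.** The paragraph starts from a directive (the blind *should* be broken for all such subjects) and a direct route (the Investigator *may* use the IWRS). It ends with a restriction (*must only*, after discussion, case by case). Because site-level unblinding is allowed only in an emergency, the restriction applies to every code break that a site is permitted to make. The situation that most needs quick access to the code is therefore the one that waits for a third party.

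What is at stake is subject safety and the workability of the procedure. An Investigator who acts alone departs from the last step. One who waits for a monitor who cannot be reached departs from the first. The text does not say which departure is acceptable.

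The protocol itself makes such emergencies foreseeable. Sections 5.3 and 6.3 guard against NSAID and sulfonamide hypersensitivity, and section 8.3.3 gives allergic bronchospasm as an example of a serious event. Three of the four arms receive active cream.

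**Working it through.** No arithmetic applies, since the point rests on no rate, effect size or error level. The check sets the sentences of section 6.6.2 against each other and looks for anything elsewhere that settles them.

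1. **Are the sentences logically incompatible?** No. The IWRS sentence names the actor and the mechanism, and does not say that the Investigator may act without prior contact. The emergency sentence can be read as a step that comes first. A site that speaks to the monitor and then uses the IWRS complies with every sentence.

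2. **What follows from that sequential reading?** The discussion is mandatory, because the wording is *must only*. If the monitor is reached, the procedure works. If not, the code may not be broken, although the first sentence says it should be. Emergency access then depends on contact with the Sponsor.

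3. **What follows from the other reading, that the Investigator may act alone?** Then the *must only* wording is wrong as it stands. The paragraph needs amending on either reading.

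4. **Who decides if the parties disagree?** Three parties are listed, separated by slashes, with no order among them. The list could mean that any one of them may decide, or that all must agree. Nothing in the section chooses.

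5. **Does another section settle it?** I looked for three things in both documents:
   - a fallback when the monitor cannot be reached: none;
   - a response time for an unblinding request: none;
   - a statement of whether the IWRS withholds the code until the discussion has taken place: none.

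6. **Number of subjects the rule covers.** The plan randomizes about 240 subjects, 60 per group, so 3 × 60 = 180 would receive active cream. The rule covers all 240, because the Investigator does not know the assignment. The documents give no expected number of emergencies.

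**The case against.** The strongest defence is that the paragraph is a sequence and that no sentence in it contradicts another. The IWRS sentence is permissive. The list of parties can be read as leaving discretion with the Investigator or treating physician. Prior discussion also discourages unnecessary code breaks, which is a legitimate aim. The contact pages and the IWRS instructions were not in the text available to me, so round-the-clock monitor cover may exist.

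Much of this stands. It rules out calling the procedures incompatible, and it rules out assuming that the monitor is unavailable out of hours. It does not supply a fallback or an order of authority. It also confirms that, read in sequence, the rule makes the code break conditional on the discussion.

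A reader might also draw three stronger conclusions that the documents do not support.

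- **That the delay could be up to 24 hours.** Protocol section 8.4 says "Serious adverse events will be evaluated by the Medical Monitor within 24 hours of receipt". That concerns the evaluation of a submitted SAE report and the planning of management and further reporting. It is not a response time for an unblinding call. Nor do the documents say how quickly the IWRS releases a code.
- **That the lack of a Data Safety Monitoring Board (section 7.9) removes a second route.** Nothing suggests that such a board would handle a site's emergency code break.
- **That involving the Sponsor harms the blind.** The discussion comes before the code is broken, so it discloses no assignment, and section 6.6.2 does not say that the Sponsor receives the code through this step.

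**Conclusion.** The concern holds as a gap in authority and access. Followed as written, section 6.6.2 makes emergency access to the code depend on reaching the Sponsor medical monitor, with no fallback, no response time for the request and no final decision-maker. This goes beyond missing detail, because the mandatory wording is itself what blocks the Investigator when contact fails.

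The size is limited. Emergencies that turn on the assignment should be rare with a topical product capped at 1.0 g per day (Protocol section 4.2). The documents do not state how long any delay would be. Sample size, power and type I error are unaffected. The amendment is still worth making, because the possible consequence for an individual subject is serious and the change is small.

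The conclusion assumes that sites would follow section 6.6.2 literally, and that no operational document outside the protocol and SAP already supplies a fallback. If one does, the protocol should point to it.

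**What to change.** Reconcile the sentences of section 6.6.2 into one procedural rule that:

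- names who has final authority over an emergency code break;
- does not make the Investigator's emergency IWRS code break depend on reaching the monitor, for example by asking for discussion beforehand where feasible and otherwise prompt notification afterwards;
- states that the notification must not disclose the assignment to personnel who are to stay blinded;
- keeps the existing record of date, time and reason.

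Check that the IWRS permissions match the amended text. This settles the code-break procedure only and proposes no change to treatment or to the handling of any event.

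The cost is about one amended sentence, the IWRS check, and slightly less Sponsor control over unnecessary code breaks. The existing documentation and deviation requirements continue to discourage those.

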## 6.7 Prior and Concomitant Therapy

Chronic medications being used at the time of the Screening and Baseline Visit, with the exception of those specified as prohibited, may be continued at the discretion of the Investigator. History of medications, therapies, and procedures are collected from the prior 6-month period for determination of eligibility. Only medications, therapies and procedures in use during the study should be entered on the eCRF.

New medications used after Baseline, required for another medical condition, that in the opinion of the Investigator will have no material impact on the study, are permitted. The addition of such a new medication during the study will be documented as a concomitant medication and the associated medical need must be recorded as an AE, if applicable.

All medications (topical, oral, prescription, over-the-counter, and herbal medications) and medical therapies or procedures that are used during the study for other diseases/conditions must be recorded on the eCRF.

The following medications are not permitted within the 60 days prior to the Baseline Visit (Visit 2) and during the conduct of the study until EOS (Visit 6):

- Masoprocol
- 5-Fluorouracil
- Cyclosporin
- Retinoids
- Trichloroacetic Acid/Lactic Acid Peel
- 50% Glycolic Acid Peel
- Topical or systemic diclofenac, celecoxib or any other NSAID (however daily low-dose aspirin is allowed, as long as the subject has been on a stable dose,  $\leq$  100 mg once a day, for 60 days prior to the start of the study.) Note: Subjects may use acetaminophen/paracetamol as needed
- Photodynamic therapy
- Topical or systemic immunomodulating agents including:
- Systemic, topical or intralesional interferon
- Imiquimod (Aldara, Zyclara)
- Topical ingenol mebutate (Picato)
- Topical tacrolimus
- Topical pimecrolimus
- Sirolimus
- Intralesional BCG
- Topical coal tar products
- Topical or systemic corticosteroids (nasal and inhaled steroids are allowable)

No pharmaceutical therapy, physical therapy or cosmetic must be applied to the selected study area throughout the entire study from Visit 1 to Visit 5, except for Investigator-approved cleanser, sunscreen, wash, and non-medicated makeup.

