### Study Schedule

	Visit 1	Visit 2	Visit 3	Visit 4	Visit 5	Visit 6 b
	Screen a	Day 1 Baseline	Week 4 b	Week 8 b	Week 12 b (End of Treatment Visit)	Week 16 (End of Study Visit)
Informed Consent	X					
Collect Demographic Data	X					
Inclusion and Exclusion Criteria	X	X				
Medical History/ Prior Medications	X	X				
Physical Examination		X			X	
Vital Signs (BP, Pulse rate)	X c	X	X	X	X	X
12-Lead EKG		X	X		X	
Hematology/Chemistry/Urinalysis		X	X		X	
Urine Pregnancy Test d	X	X	X	X	X	X
AK lesion count and measurements	X	X	X	X	X	X
Safety and Local Tolerability Evaluation		X	X	X	X	X
Randomization		X				
Dispense Study Product (as needed)		X	X	X		
Dispense/Review/Collect Study Diary		X	X	X	X	X
Diagram Affected Areas to be Treated c		X	X	X		
Review Subject Instructions		X	X	X	X	
Initiate Treatment Subjects will treat the affected areas under supervision for the first time		X				
Collect Study Product			X	X	X	
Evaluate Compliance			X	X	X	
Adverse Event Assessment/Collection		X	X	X	X	X
Concomitant Medications		X	X	X	X	X
End of Study						X

aUp to 60 days before Visit 2.

bAllowed visit window  $\pm$  5 days.

cRecord on source only. Only a single contiguous 5 cm x 5 cm area will be treated per subject.

dFor female subjects of childbearing potential.

---

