### 4.2 Discussion of Design

The study consists of three phases: Screening (up to 60 days), Treatment (12 weeks) and Follow-Up (4 weeks). In Groups 2 and 4, the randomized investigational products will be applied twice daily for 12 weeks to cover the entire single contiguous 5 cm x 5 cm (25 cm^2) lesional area on the face and/or scalp. In Groups 1 and 3, the randomized active DFD-07 (celecoxib) Cream product will be applied only in the evening, while the Vehicle for DFD-07 Cream will be applied in the morning to keep the blinding between groups.

Subjects in all the groups will undergo a further 4-week treatment-free period from Week 12 to Week 16 (End of Study).

The investigational products will be applied twice daily for 12 weeks to cover the entire lesional area (5 cm x 5 cm) on the face and/or scalp identified by the Investigator for treatment. The dose for the study product will be a maximum of 0.5 g per application to the entire 5 cm x 5 cm area on the face and/or scalp for a maximum dose of 1.0 g per day.

Subject visits are scheduled at Screening (Visit 1), Baseline (Visit 2 - Day 1), and Weeks 4 (Visit 3), 8 (Visit 4), 12 (Visit 5) and 16 (Visit 6). Clinical determinations of efficacy will be conducted based on clinically visible or palpable lesions of AK in the treated areas at Weeks 4, 8, 12 and 16 in comparison to Baseline. Comparisons will be made between the different strengths and dosing regimens of DFD-07 (celecoxib) Cream and Vehicle Cream.

Local cutaneous tolerability will be determined at Visits 2 – 6 for the entire treated area. Other safety assessments include physical examinations (HEENT, lungs, heart, abdomen, skin,

---

neurologic), laboratory assessments, electrocardiogram (EKG), vital signs (blood pressure, pulse rate), urine pregnancy tests, and collection of adverse event data.

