- Retinoids (oral and topical)
- Trichloroacetic Acid/Lactic Acid Peel
- 50% Glycolic Acid Peel
- Topical or systemic diclofenac, celecoxib or any other NSAID (however daily low-dose aspirin is allowed, as long as the subject has been on a stable dose,  $\leq 100$  mg once a day, for 60 days prior to the start of the study.) Note: Subjects may use acetaminophen/paracetamol as needed
- Photodynamic therapy
- Topical or systemic immunomodulating agents
- Systemic, topical or intralesional interferon
- Imiquimod (Aldara, Zyclara)
- Topical ingenol mebutate (Picato)
- Topical tacrolimus
- Topical pimecrolimus
- Sirolimus
- Intralesional BCG
- Topical coal tar products
- Topical or systemic corticosteroids (nasal and inhaled steroids are allowable)

7. Subjects must agree not to use any product on the treatment area during the entire course of study except for Investigator-approved cleanser, sunscreen, wash, and non-medicated make-up. Subjects should continue to use these Investigator-approved products for the duration of the study and should avoid any changes in these consumer products.

8. Subjects must be willing to comply with sun avoidance measures for the face including use of Investigator-approved sunscreen and/or hats, have limited sun exposure time, and have no tanning bed use.

9. Subjects must be in good general health as determined by the Investigator and supported by the medical history, and normal or not clinically significant abnormal vital signs (blood pressure and pulse rate). Subjects are eligible if:

- Systolic blood pressure (BP)  $< 160$  and  $> 85$  mmHg
- Diastolic BP  $< 100$  and  $> 50$  mmHg

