### **5.3 Exclusion Criteria**

1. Known or suspected hypersensitivity to any non-steroidal anti-inflammatory drugs (NSAID) or any component of the formulation of the study medication, including a history of asthma, urticarial, or other allergic-type reactions after taking aspirin or other NSAIDs.
2. Known or suspected allergy to sulfonamides.

3. Clinical evidence of severe, uncontrolled autoimmune, cardiovascular, gastrointestinal, hematological, hepatic, neurologic, pulmonary or renal disease.
4. Recent (within 6 months) or planned coronary artery bypass graft surgery.
5. Significant history (within the past year) of alcohol or drug abuse.
6. Participation in any clinical research study within 30 days of the Baseline Visit.
7. Concomitant use of cosmetics or other topical drug products on or near the selected treatment area, except for Investigator-approved cleanser, sunscreen, wash, and non-medicated makeup.
8. Cosmetic or therapeutic procedures (e.g. laser, peeling, photodynamic therapy) within 2 weeks and within 2 cm of the selected treatment area.
9. Other skin conditions within the selected treatment area (e.g. rosacea, psoriasis, atopic dermatitis, eczema, basal or squamous cell carcinoma or albinism).
10. Use of sun lamps, tanning beds, and tanning booths during the 14 days prior to the Baseline Visit or planned use during the study.
11. Any systemic cancer therapy or diagnosis within 6 months of the Baseline Visit.
12. Females who are pregnant or lactating or planning to become pregnant during the study period.
13. Subjects may not have a personal relationship with any member of the study staff or be part of the staff at the medical practice.
14. Subjects who are unable to comply with the study requirements for any reason.

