#### **7.10.6 Visit 6 – Week 16/End of Study Visit (Allowed visit window is $\pm$ 5 days)**

1. Evaluate protocol compliance and record any deviations.
2. Investigator is to document the size and location of the lesions with in the treatment area and on a grid foil. One copy of the grid foil should be inserted into the subject's source document.
3. Collect vital signs (blood pressure and pulse rate).
4. Conduct a urine pregnancy test for all females of child bearing potential.
5. Collect AE data. This includes a review of the diary card for potential AEs.
6. Complete eCRF.

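### Section 6.7 ends the study-area therapy ban at Visit 5, so no text expressly bars cryosurgery, curettage or laser in the four weeks before the primary count

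*Protocol*

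**What the plan says.** Protocol 6.7 contains two on-study bans with different end dates.

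- The list of named agents may not be used "during the conduct of the study until EOS (Visit 6"). It covers drugs, photodynamic therapy (PDT) and two types of acid peel. Cryosurgery, curettage and laser are not on it.
- The general sentence after the list keeps drug treatment, physical therapy and cosmetics off the selected area "throughout the entire study from Visit 1 to Visit 5", apart from approved cleanser, sunscreen, wash and plain make-up.

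Visit 5 is Week 12, the end of treatment (7.10.5). The primary endpoint is counted at Visit 6, Week 16 (Protocol 3.1, SAP 1.3.1) and requires that no AK lesion can be seen or felt in the treatment area.

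Other text bears on Weeks 12 to 16:

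- Section 4.2 has every group undergo a "further 4-week treatment-free period from Week 12 to Week 16 (End of Study").
- Inclusion 7: "Subjects must agree not to use any product on the treatment area during the entire course of study".
- Exclusion 8: "Cosmetic or therapeutic procedures (e.g. laser, peeling, photodynamic therapy) within 2 weeks and within 2 cm of the selected treatment area".
- Recording, in 6.7: "Only medications, therapies and procedures in use during the study should be entered on the eCRF". The Study Schedule marks "Concomitant Medications" at Visit 6, and 7.10.6 opens with "Evaluate protocol compliance and record any deviations".

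**The concern.** The general ban claims to cover the whole study and then stops one visit short. The four weeks it leaves out are the ones that end at the primary count.

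The incentive to intervene is real. The Introduction describes removal of AK on diagnosis as standard care and gives cryosurgery and curettage as examples. Study treatment stops at Week 12, so a subject with remaining lesions at that visit is an obvious candidate for removal. If all of that subject's lesions were ablated before Week 16, the primary assessment would find none. The subject would be scored as a complete clearance, because SAP 2.6 has no rule for such a case and the ITT set is primary.

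What is at stake is that the primary count could then credit the cream or the vehicle with clearance achieved by another method.

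**Working it through.** **Step 1: does any rule expressly cover cryosurgery, curettage or laser on the area in Weeks 12 to 16?**

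- *6.7, named list.* Right dates (to Visit 6), but these three procedures are not named.
- *6.7, general sentence.* Ends at Visit 5. It reaches the three procedures at all only if the words physical therapy include them.
- *Inclusion 7.* Right dates, but it concerns products, not procedures.
- *Exclusion 8.* Names laser, but it is an entry criterion. Section 7.10.1 ties its window to the 2 weeks before Baseline.
- *4.2, treatment-free period.* Describes the follow-up phase and shows intent, but lists no prohibitions.
- *Per-protocol criterion 2 (Protocol 11.2.2, SAP 2.2).* Concerns prohibited medications.
- *General per-protocol wording.* Excludes activity that could have interfered with evaluating efficacy. It could remove an ablated subject from PP, but does not touch ITT.

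None expressly does.

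**Step 2: is recording covered?** Mostly, by the 6.7 eCRF rule, the schedule row and the Visit 6 deviation check. Two small weaknesses remain. The 7.10.6 steps omit the concomitant medication update that Visits 3 to 5 include. And a procedure that is not clearly prohibited need not be logged as a deviation.

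**Step 3: the plan's own sample size.** Inputs from Protocol 11.1: 45% versus 20%, power 80%, α 0.05, drop-out 10%. Two-sided, without continuity correction, with p̄ = 0.325:

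n = [1.960·√(2·0.325·0.675) + 0.842·√(0.45·0.55 + 0.20·0.80)]² / 0.25² = (1.298 + 0.537)² / 0.0625 ≈ 53.9, so 54 per group.

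54/0.90 = 60. Both stated figures reproduce. The one-sided equivalent is 43, so the stated size fits a two-sided test, while the hypotheses in SAP 2.6 are one-sided. Both versions are shown below.

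**Step 4: illustration of scale.** The documents give no ablation rate, so *f* is an assumption: the fraction of subjects in an arm who would not otherwise be clear at Week 16, whose lesions are all ablated in the window, and who are all counted as clear.

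Observed rate = p + f(1 − p). With the same f in both arms, the difference is 25 × (1 − f) points.

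Power is the exact binomial probability of rejection with 60 per arm and the SAP 2.1 test rule (Pearson if every cell is at least 5, otherwise Fisher).

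| f active | f Vehicle | Rates | Difference (points) | Power, two-sided | Power, one-sided |
|---|---|---|---|---|---|
| 0 | 0 | 45% v 20% | 25.0 | 84.8% | 91.0% |
| 4% | 4% | 47.2% v 23.2% | 24.0 | 79.7% | 88.0% |
| 10% | 10% | 50.5% v 28.0% | 22.5 | 72.4% | 83.1% |
| 0 | 5% | 45% v 24% | 21.0 | 68.7% | 79.4% |
| 5% | 0 | 47.75% v 20% | 27.75 | 90.8% | 95.1% |

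In subjects, 4% in both arms is 60 × 0.55 × 0.04 = 1.3 active and 60 × 0.80 × 0.04 = 1.9 Vehicle. At 10% it is 3.3 and 4.8. With equal fractions, power falls to 80% at f of about 3.8% two-sided or 13.5% one-sided.

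The difference is inflated only when 0.55·f(active) exceeds 0.80·f(Vehicle), that is, when the active fraction is more than 0.80/0.55 = 1.45 times the Vehicle fraction. Otherwise it is unchanged or diluted.

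**The case against.** The strongest reply is that nobody chose this. The same sentence says the entire study, the named list runs to Visit 6, inclusion 7 runs for the whole study, and the follow-up is called treatment-free. An investigator who reads these together is unlikely to think that lesions may be ablated before the primary count. That stands. A reader might infer that the protocol permits ablation after Week 12. It does not; it only fails to bar it expressly.

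A reader might also take the general sentence as the sole on-study ban that reaches any physical procedure. That goes too far, because PDT and the peels are procedures and stay barred to Visit 6. The gap is limited to procedures not on that list.

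The safeguards deserve credit. The general per-protocol wording could exclude an ablated subject, and SAP 2.1 requires signed data-handling decisions before database lock. Neither prespecifies how the primary ITT analysis would score that subject.

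Finally, the power figures are hypothetical. They assume total clearance of every ablated subject, and the two-sided column is the less favourable one given the one-sided hypotheses. That also stands. Nothing in the documents makes any of the assumed rates likely.

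**Conclusion.** The point holds as a minor wording defect in an operative rule that protects the primary endpoint. The contradiction in 6.7 is certain, and so is the absence of any express bar on cryosurgery, curettage or laser in the area during Weeks 12 to 16.

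The effect on the result is not established. A few ablated subjects per arm would be enough to matter under the planning rates, but the documents do not say whether there would be any, or in which arm. It would therefore be wrong to infer that the primary comparison is biased, or biased in favour of the cream. Equal use in both arms dilutes the difference.

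It would also be wrong to conclude that such procedures would go unrecorded, since recording is largely provided for.

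**What to change.** In Protocol 6.7, change Visit 5 to Visit 6 (EOS), and state that cryosurgery, curettage, laser and other lesion-directed procedures in the treatment area are prohibited through Visit 6. Both parts are needed: if physical therapy does not include ablation, moving the date alone closes nothing.

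For alignment with the schedule only, add the concomitant medication update, including procedures, to the 7.10.6 steps, with the date of any AK-directed procedure in the area.

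Optionally, prespecify in SAP 2.6 a sensitivity analysis that scores as not cleared any subject who has a non-study AK procedure in the area before the Week 16 count. This is an estimand choice, not a correction.

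The cost is one visit number and a few words in 6.7, one line in 7.10.6 and, if wanted, one SAP sentence. No visit, assessment or subject is added.
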